11.5 Safety and Tolerability Assessments

11.5.1 Adverse Events

A baseline sign and symptom is defined as an AE that starts after the subject has provided written informed consent and that resolves prior to the first dosing occasion, or an AE that starts prior to the first dosing occasion and does not increase in severity after dosing. A treatment-emergent AE (TEAE) is defined as an AE that occurs postdose or that is present predose and becomes more severe postdose. If the start date of an AE is incomplete or missing, it will be assumed to be a TEAE, except if the incomplete start date or the stop date indicates that the event started prior to the first dosing. The AE of special interest (AESI) for this study are defined as follows:

• Clinically significant peripapillary or optic disc swelling on funduscopic examination, as determined by the local site principal investigator/ophthalmologist

- Clinically significant functional visual change from baseline, as determined by the local site principal investigator/ophthalmologist
- Cases of potential drug-induced liver injury that include an elevated alanine aminotransferase or aspartate aminotransferase in combination with either an elevated bilirubin or clinical jaundice, as defined by Hy's Law
- Suspected transmission of an infectious agent by the study drug as defined below:
 - Any organism, virus, or infectious particle (e.g., prion protein transmitting transmissible spongiform encephalopathy), pathogenic or non-pathogenic, is considered an infectious agent. A transmission of an infectious agent may be suspected from clinical symptoms or laboratory findings that indicate an infection in a subject exposed to a medicinal product. The term applies only when a contamination of the study drug is suspected.

AEs occurring during administration of the Period 1 Day 1 dose up to the dose administration in Period 2 Day 1 will be assigned to Period 1. Any AEs occurring during administration of the Period 2 Day 1 dose and postdose from Period 2 Day 1 to Follow-up will be assigned to Period 2.

All AEs will be listed by study part. The TEAEs will be summarized by study part, treatment, severity rated based on WHO Toxicity Grading Scale, and relationship to the study drug. The frequency (the number of TEAEs, the number of subjects experiencing a TEAE, and the percentage of subjects experiencing a TEAE) of TEAEs will be summarized by study part, treatment, and by Medical Dictionary for Regulatory Activities system organ class and preferred term. The summary and frequency TEAE tables will be presented for all causalities and for those TEAEs considered related to the study drug (those that have a relationship of suspected). Any severe or serious AEs or any AESIs or deaths will be tabulated by study part. For any AEs that change severity ratings the AE will be included only once under the maximum severity rating in the summaries.

11.5.2 Clinical Laboratory Parameters

All chemistry, hematology, coagulation and urinalysis data outside the clinical reference ranges will be listed by study part, parameter and treatment.

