9.1 SAFETY AND TOLERABILITY ANALYSIS

Safety will be assessed by a review of AEs, physical examinations, vital signs, clinical laboratory assessments, ophthalmologic assessments, and ECGs. Clinical laboratory assessments, vital signs (including oral temperature, respiratory rate, and supine blood pressure and pulse), weight data, ophthalmologic assessments, and ECGs will be listed by subject number and scheduled time. Changes from baseline will be summarized.

Verbatim descriptions of AEs will be coded according to current Medical Dictionary for Regulatory Activities version 20.0 (or higher) guidelines. Adverse events will be summarized. Adverse events of special interest that could indicate hypersensitivity reactions will be summarized separately. Enrollment and discontinuations from the study will be summarized overall. Demographics and baseline characteristics such as age, sex, and BMI will be summarized overall.

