6.2 Safety Endpoints

The safety endpoints of this study are:

• Incidence, nature, and severity of adverse events (AEs)

• Changes in vital signs, electrocardiograms (ECGs), physical examination findings, ophthalmology assessment findings, and clinical laboratory results during and following GDC-0134 administration

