11 STATISTICAL METHODOLOGY

11.1 General

Data listings will be provided for the All Subjects Population. Summary statistics and statistical analyses will be performed for subjects included in the relevant analysis populations (Safety/PK).

For continuous data, summary statistics will include the arithmetic mean, arithmetic standard deviation (SD), median, minimum, maximum, and number. For log-normal data (e.g., the PK parameters: AUCs and C_{max}), the geometric mean and geometric coefficient of variation (CV) will also be presented. For categorical data, frequency counts and percentages will be presented. Data listings will be provided for all subjects up to the point of withdrawal, with any subjects excluded from the relevant population highlighted. For the calculation of summary statistics and statistical analysis, unrounded data will be used.

Missing values will not be imputed, with the possible exception of missing PK predose concentrations, as detailed in Section 11.4.2.

Data analysis will be performed using SAS® Version 9.4.

Analysis Data Model (ADaM) datasets will be prepared using Clinical Data Interchange Standards Consortium (CDISC) ADaM Version 2.1, and CDISC ADaM Implementation Guide Version 1.1. Pinnacle 21 Community Validator Version 2.2.0 will be utilized to ensure compliance with CDISC standards.

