11.5.3 Vital Signs

Vital signs values outside the clinical reference ranges will be flagged on the individual subject data listings.

The vital signs data will be summarized by study part and treatment, together with changes from baseline. Figures of mean vital signs and mean change from baseline profiles will be presented by study part and treatment.

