11.5.4 Electrocardiogram

The ECG data will be obtained directly from the 12-lead ECG traces. These data include the QT interval calculated using the Fridericia correction (QTcF), the PR and QT intervals, the QRS duration, and heart rate.

Where ECGs are measured in triplicate (at approximately 2-minute intervals), the mean value will be used in all subsequent calculations.

Values for ECG parameters outside the clinical reference ranges will be flagged on the individual subject data listings.

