11.5.6 Other Assessments

All other safety assessments not detailed in this section will be listed but not summarized or statistically analyzed.

Medical history data will be presented.

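### The only laboratory output stated in the SAP is a listing of out-of-range values; the full listing and change-from-baseline summary in Protocol 9.1 are not carried over, and no change is declared

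*SAP*

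**What the plan says.** Protocol 9.1 names laboratory data first among the safety data to be listed: "Clinical laboratory assessments, vital signs (including oral temperature, respiratory rate, and supine blood pressure and pulse), weight data, ophthalmologic assessments, and ECGs will be listed". The same passage gives the listing keys and a second output: these data "will be listed by subject number and scheduled time. Changes from baseline will be summarized". Neither output is limited by reference range.

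SAP 11.5.2 consists of one sentence: "All chemistry, hematology, coagulation and urinalysis data outside the clinical reference ranges will be listed by study part, parameter and treatment". It adds a range criterion, no longer names subject and scheduled time as keys, and mentions no summary.

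The neighbouring SAP sections are worded differently. For vital signs (11.5.3), "Vital signs values outside the clinical reference ranges will be flagged on the individual subject data listings", and the data are also summarized with changes from baseline. For ECGs (11.5.4), "Values for ECG parameters outside the clinical reference ranges will be flagged on the individual subject data listings". In both, range decides what is flagged, not what is listed.

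SAP 6.2 includes among the safety endpoints changes in "ophthalmology assessment findings, and clinical laboratory results during and following GDC-0134 administration". SAP 11.1.1 defines a period-specific baseline that expressly covers laboratory parameters. SAP 4 says that the SAP supersedes the protocol's statistical text and will identify substantial differences. SAP 13 reports none.

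**The concern.** A change from baseline needs two values. The one laboratory output the SAP states drops a value whenever it is in range, and no group summary makes up for it. The baseline defined in SAP 11.1.1 is used by no stated laboratory output.

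In healthy volunteers this affects most of the data. Inclusion criterion 3 (Protocol 5.3) and the Check-in rule (Protocol 5.2) require results within range unless the investigator judges them not clinically significant, so period baselines are mostly in range by design. An abnormal post-dose value would often be listed without its baseline, and a shift that stays within range would not be listed at all. For Days 36 and 43, a missing row could mean a normal result or a test not done.

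Some of the effects the protocol watches for could first appear as shifts. Protocol 6.1.4.9 describes 2- to 4-fold increases in unconjugated bilirubin in rats without raised liver enzymes, and Protocol 6.1.4.8 describes possible interference with glycemic regulation. At stake is whether the study report can describe a stated safety endpoint.

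**Working it through.** No power, error-rate or event figure is involved, and the plan gives no figure of its own to reproduce. The check sets the texts side by side and then reads them against the visit schedule.

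**1. Stated outputs**

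| Data | Protocol 9.1 | SAP |
|---|---|---|
| Laboratory | Listed by subject and time; changes summarized | 11.5.2: out-of-range values listed by part, parameter and treatment |
| Vital signs | Same | 11.5.3: out-of-range values flagged on subject listings; values and changes summarized |
| ECG | Same | 11.5.4: out-of-range values flagged on subject listings |

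**2. Does another SAP section supply the missing laboratory output?**

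- SAP 11.5.6: "All other safety assessments not detailed in this section will be listed but not summarized or statistically analyzed". Laboratory data are detailed in 11.5.2, so this catch-all does not reach them.
- SAP 11.1: "Data listings will be provided for the All Subjects Population". This fixes the population for listings, not which laboratory values they contain.
- SAP 11.1.1 defines the laboratory baseline but no output that uses it.
- SAP 11.1.2 says unscheduled readings, laboratory ones included, are labelled in the listings. It also bars them from summaries except as baseline, so listings are their main outlet. Under 11.5.2, an unscheduled retest that returned to range would not be listed.
- SAP 13 declares no departure from the protocol.

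None of these states a full laboratory listing or a laboratory summary of change.

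**3. The schedule (Protocol Tables 7-1 and 7-2)**

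Chemistry, blood count and urinalysis are drawn at Screening and on Days -1, 21, 36 and 43. This agrees with the 5 draws in Protocol Appendix B. Dosing is on Days 1 and 22. The scheduled changes from period-specific baseline are therefore:

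- Period 1: Day 21 minus Day -1.
- Period 2: Day 36 minus Day 21, and Day 43 minus Day 21.

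Day 21 enters all three. If the Day 21 value is in range and unlisted, none of the three changes can be calculated from the listing. Coagulation is drawn only at Screening and on Days -1 and 21 (3 draws in Appendix B), so Day 21 is its only scheduled post-dose sample.

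**4. Size, per part, assuming all 22 subjects attend every visit**

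- All draws: 22 × 5 = 110.
- Post-dose draws: 22 × 3 = 66.
- Scheduled post-dose chemistry results, with the 18 analytes in Appendix A: 66 × 18 = 1,188.

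Each of the 1,188 defines one change from baseline, and the SAP states a summary for none. How many would be listed depends on the out-of-range rate, which the documents do not give. It is assumed here:

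| Assumed rate | Listed | Not listed |
|---|---|---|
| 2% | 1,188 × 0.02 ≈ 24 | 1,164 |
| 5% | 1,188 × 0.05 ≈ 59 | 1,129 |
| 10% | 1,188 × 0.10 ≈ 119 | 1,069 |

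**5. Illustration**

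Assume an upper limit of normal of 40 U/L for ALT. A rise from 10 to 38 U/L is 38 / 10 = 3.8-fold and would be listed at neither visit.

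**The case against.** The strongest reply is that 11.5.2 says out-of-range data will be listed and nowhere says in-range data will not. SAP 11.1 promises listings for all subjects, 11.1.2 presupposes listings that carry unscheduled laboratory results, and SAP 4 says the analyses generally follow the protocol and refers the detailed outputs to a shell document. On that reading, the full listing in Protocol 9.1 stands and 11.5.2 merely describes an extra listing of abnormal values. The contrast with vital signs and ECGs is also less sharp than it looks, since those sections refer to subject listings without announcing them.

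Much of this stands. That the listing contains only out-of-range values is an inference, and the shells may settle it. The reply does not cover the summary of change, however. SAP 11.5.3 states one for vital signs and 11.5.2 states none for laboratory data.

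A reader might infer that in-range results appear nowhere in the plan. The documents do not support that, because Protocol 9.1 states both outputs; the gap is in the SAP.

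A reader might also infer that a serious liver or platelet signal would be missed. That is not supported either. Values meeting the criteria in Protocol 8.3.1.6 are out of range and so would be listed, as would a platelet count like that in the life-threatening case in Protocol 2.2. Under Protocol 8.3.1.4 the investigator reviews all laboratory findings. Cases meeting the liver criteria go to the sponsor within 24 hours, and SAP 11.5.1 tabulates events of special interest. An out-of-range baseline would itself be listed, and Check-in requires laboratory results before a subject continues, so a missing baseline row in a dosed subject most plausibly means in range.

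**Conclusion.** The point holds as a gap between the protocol and the SAP's stated outputs. For laboratory data the SAP states neither the full listing nor the change-from-baseline summary in Protocol 9.1, and it does not declare the difference. Followed as written, it does not deliver the endpoint of change in laboratory results. It should be corrected before the SAP is finalized, which SAP 4 requires before database lock.

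The firm part of the size is the schedule: three changes from baseline per subject, part and analyte for chemistry and blood count, all depending on Day 21, with no stated summary. The counts of unlisted results rest on the assumed 2% to 10% rate and on full attendance; the conclusion does not depend on them.

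The documents do not show that in-range results will be absent from the study report. The shells were not available, and the results remain in the database. The point concerns reporting of a safety endpoint for which no inferential analysis is planned. It does not concern subject protection during the study.

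**What to change.** Reword SAP 11.5.2 along these lines:

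> All chemistry, hematology, coagulation and urinalysis results, scheduled and unscheduled, are listed by study part, subject, parameter and timepoint, with the period baseline identified and out-of-range values flagged. For numeric parameters, values and changes from period-specific baseline are summarized by study part and treatment. Out-of-range results are also presented as a separate extract.

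The first sentence restores the Protocol 9.1 listing and the second its summary; the third keeps the current SAP output. Align the shells with the new text. If they already contain these outputs, the edit only brings the SAP into line with them. If the reduced output is intended, state and justify it in SAP 13 instead.

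The cost is a few SAP sentences, a longer listing and one additional set of summary tables, all from data already collected. No visit, sample or assay is added.

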11.5.3 Vital Signs

Vital signs values outside the clinical reference ranges will be flagged on the individual subject data listings.

The vital signs data will be summarized by study part and treatment, together with changes from baseline. Figures of mean vital signs and mean change from baseline profiles will be presented by study part and treatment.

11.5.4 Electrocardiogram

The ECG data will be obtained directly from the 12-lead ECG traces. These data include the QT interval calculated using the Fridericia correction (QTcF), the PR and QT intervals, the QRS duration, and heart rate.

Where ECGs are measured in triplicate (at approximately 2-minute intervals), the mean value will be used in all subsequent calculations.

Values for ECG parameters outside the clinical reference ranges will be flagged on the individual subject data listings.

11.5.5 Ophthalmological Assessments

Ophthalmological assessments include fundoscopic examination, visual acuity assessment, and visual field examination. The ophthalmological data will be listed by study part.

11.5.6 Other Assessments

All other safety assessments not detailed in this section will be listed but not summarized or statistically analyzed.

Medical history data will be presented.

11.5.7 Safety and Tolerability Statistical Methodology

No inferential statistical analyses are planned.

12 INTERIM ANALYSES

Given the hypothesis-generating nature of this study, the sponsor may choose to conduct interim analyses. The decision to conduct an optional interim analysis and the timing of the analysis will be documented in the sponsor's trial master file prior to the conduct of the interim analysis. The interim analysis will be performed and interpreted by the sponsor study team personnel.

13 CHANGES FROM THE PROTOCOL SPECIFIED STATISTICAL ANALYSES

There were no changes from the protocol-specified statistical analyses.

14 DATA PRESENTATION

14.1 Insufficient Data for Presentation

Some of the TFLs may not have a sufficient number of subjects or data for presentation. If this occurs, the blank TFL shell will be presented with a message printed in the center of the table, such as, "No serious adverse events occurred for this study."

